**AMENDMENT HISTORY**

Version	Date	Description
1.0	19 February 2018	Initial version
2.0	30 May 2018	Amendment 1 (this document)

**The overall rationale for Amendment 1:** The purpose for this amendment is to align all the statistical analyses of Phase 2 and 3 Ebola studies and to address the remarks from the Food and Drug Administration (FDA). The changes made together with the rationale for each change are as follows:

---

**Rationale:** The Day 181 analysis window has been replaced with the “≥Day 99” window to align with the sensitivity analysis. The 180 days post-boost analysis window for the immunogenicity analysis set is also updated to ensure that data points in the corresponding window for the per protocol analysis are also included.

### 2.1. Analysis Visit Windows and Periods

---

**Rationale:** Immunogenicity assessments after a planned but not administered dose will only be shown in data listings and not included in tabulations and graphs.

### 2.3 Analysis Sets

---

**Rationale:** A text is added to clarify that dot plots will be generated for both ELISA and VNA.

#### 6.2.1.3 Analysis Methods

---

**Rationale:** Definitions for the sample interpretation for cellular data have been updated. The definition of “responder” for the cellular assay has also been updated due to lack of information on the assay characteristics.

##### 6.2.2.1. Parameters

---

**Rationale:** A text is added to clarify that tabulations of SAEs, AEs with fatal outcome, AEs leading permanent discontinuation from boost vaccination, Grade 3 AEs and IREs will be presented by System Organ Class (SOC) and Preferred Term (PT).

#### 7.1.3. Analysis Methods

---

**Rationale:** It is clarified that imputation of missing end dates of ongoing AEs will only be used to derive the duration of the events. Nevertheless, all missing AE end dates will be kept as unknown in the analysis dataset and listings.

### Attachment 1: PERIOD ALLOCATION OF ADVERSE EVENTS

---

**Rationale:** It is clarified that tabulations of solicited AEs will count each event once (ie, assigning the highest grade and the relatedness that most implicates the vaccine) within an analysis period and that there will not be multiple listings of the same AE on the same day.

### Attachment 2: TRANSFORMING ON-SITE ASSESSMENTS AND DIARIES OF

---

**SOLICITED ADVERSE EVENTS INTO AN ANALYSIS FORMAT**

---

**Rationale:** Minor editorial changes have been made throughout the document.

---

## ABBREVIATIONS

Ad26	adenovirus serotype 26 (vector)
Ad26.ZEBOV	adenovirus serotype 26 expressing the Ebola virus Mayinga glycoprotein
AE	adverse event
aMLV	amphotropic Murine Leukemia Virus
BMI	body mass index
CI	confidence interval
(e)CRF	(electronic) case report form
CTP	clinical trial protocol
DMID	Division of Microbiology and Infectious Diseases
EBOV	Ebola virus
ELISA	enzyme-linked immunosorbent assay
EU	European Union
FANG	Filovirus Animal Nonclinical Group
FDA	Food and Drug Administration
GP	glycoprotein
IC 50	50% inhibitory concentration
ICF	informed consent form
ICH	International Council for Harmonisation
ICS	intracellular cytokine staining
IDMC	Independent Data Monitoring Committee
IFN- $\gamma$	interferon- $\gamma$
IL	interleukin
InfU	infectious units
IRE	immediate reportable event
LLOQ	lower limit of quantification
MedDRA	Medical Dictionary for Regulatory Activities
MVA	Modified Vaccinia Ankara
MVA-BN-Filo	Modified Vaccinia Ankara - Bavarian Nordic vector expressing the glycoproteins of Ebola virus, Sudan virus and Marburg virus and the nucleoprotein of Tai Forest virus (formally known as Côte d'Ivoire ebolavirus )
NSAID	non-steroidal anti-inflammatory drug
PBMC	peripheral blood mononuclear cells
PT	Preferred Term
SAE	serious adverse event
SAP	statistical analysis plan
SFU	spot-forming units
SOC	System Organ Class
TAFV	Tai Forest virus
TNF- $\alpha$	tumor necrosis factor- $\alpha$
VNA	virus neutralization assay
vp	viral particles
WHO	World Health Organization
ZEBOV	Zaire ebolavirus

## 1. INTRODUCTION

This is the statistical analysis plan (SAP) for the VAC52150EBL2001 study. It describes the final analysis (when all subjects have completed the last study-related visit or discontinued earlier) to be performed.

Note that vaccination was halted in this study following a case of Miller Fisher syndrome after receipt of Modified Vaccinia Ankara Bavarian Nordic vector expressing multiple filovirus proteins (MVA-BN-Filo) or placebo. Therefore, there were delays in scheduled boost vaccinations for some subjects. Due to this delay, an initially planned primary analysis (when all subjects have completed the 6-month post-boost visit or discontinued earlier) was not performed.

### 1.1. Trial Objectives

#### Primary Objective

The primary objective is to assess the safety and tolerability of 3 vaccination schedules of adenovirus serotype 26 expressing the Ebola virus Mayinga glycoprotein (Ad26.ZEBOV) and MVA-BN-Filo administered intramuscularly as heterologous prime-boost regimens on Days 1 and 29, Days 1 and 57, or Days 1 and 85.

#### Secondary Objectives

The secondary objectives are:

- To assess humoral immune responses, as measured by enzyme-linked immunosorbent assay (ELISA), to the Ebola virus (EBOV) glycoprotein (GP) 21 days post boost of 3 vaccination schedules of Ad26.ZEBOV and MVA-BN-Filo administered intramuscularly as heterologous prime-boost regimens on Days 1 and 29, Days 1 and 57, or Days 1 and 85 (Groups 1-3).
- To assess safety and tolerability after Ad26.ZEBOV vaccination administered (at a dose of  $5 \times 10^{10}$  viral particles [vp]) intramuscularly on Day 1 (Group 4, vector shedding in France).

In addition, several exploratory objectives were specified in the clinical trial protocol (CTP) and will be investigated if corresponding outcome measures are available.

### 1.2. Trial Design

This was a randomized, observer-blind, placebo-controlled, parallel-group, multicenter, Phase 2 study to evaluate the safety, tolerability and immunogenicity of 3 heterologous prime-boost regimens using Ad26.ZEBOV at a dose of  $5 \times 10^{10}$  vp as prime and MVA-BN-Filo at a dose of  $1 \times 10^8$  infectious units (Inf U, nominal titer) as boost at a 28-, 56- or 84-day interval in healthy adult subjects in Europe (United Kingdom [UK] and France). The 3 prime-boost regimens only differed in the timing of the boost vaccination (ie, 28, 56 or 84 days after prime, respectively referred to as Groups 1, 2 and 3), while the dose of each study vaccine (Ad26.ZEBOV, MVA-BN-Filo or placebo) and the sequence of vaccination were identical. In an additional group (Group 4) in France, Ad26 vector shedding, safety, tolerability and immunogenicity following a single vaccination with Ad26.ZEBOV at a dose of  $5 \times 10^{10}$  vp was evaluated.

The subject population consisted of healthy men and women aged between 18 and 65 years (inclusive), who never received a candidate Ebola vaccine before and had no prior exposure to Ebola virus (including travel to West Africa less than 1 month prior to screening) or a diagnosis of Ebola virus disease.

At study entry, subjects were offered the option to enroll into Cohorts I (open-label), II, or III in the UK or into Cohorts II or III, or Group 4 in France. In Cohorts II and III in both countries, core immunogenicity assessments (humoral and cellular assays) were performed. In Cohort II in both countries, additional immunogenicity assessments were done. In Cohort I, plasmablast response kinetics were evaluated for the determination of the optimal sampling time points of the B-cell response as part of the additional immunogenicity assessments in Cohort II in the UK. In the UK, Cohorts I and III started in parallel, while Cohort II in the UK only started when the peak of B-cell response after prime vaccination in Cohort I was identified. In France, Cohorts II and III started in parallel (as there was no Cohort I) and were independent of Cohort I in the UK. In Group 4, immunogenicity assessments (humoral assays) and Ad26 vector shedding assessments were performed. Below is a schematic overview of the study design. For further details, see Section 3 of the CTP.

#### Groups 1-3

Study Cohorts	Randomization Ratio (Active:Placebo)	Group 1 N=204	Group 2 N=204	Group 3 N=204	Cohort Total N=612	UK N=321	France N=291
Cohort I	-	10/0	10/0	10/0	30	30	-
Cohort II	14:1	84/6	84/6	84/6	270	135	135
Cohort III	10:3	80/24	80/24	80/24	312	156	156

#### Group 4

Randomization Ratio (Active:Placebo)	Group 4 N=18	Group Total N=18	UK N=0	France N=18
5:1	15/3	18	-	18

Groups 1, 2, and 3: prime on Day 1, followed by boost 28, 56 or 84 days after prime, respectively. Group 4: vaccination on Day 1; N: number of subjects to receive study vaccine (Ad26.ZEBOV, MVA-BN-Filo or placebo)

### 1.3. Statistical Hypotheses for Trial Objectives

As this study is designed to provide descriptive information regarding safety and immunogenicity without formal vaccination schedule comparisons, no formal statistical hypothesis testing will be performed.

### 1.4. Sample Size Justification

An originally planned sample size of 612 subjects were to substantially contribute to the overall safety database of the Ad26.ZEBOV and MVA-BN-Filo prime-boost regimens. An additional 18 subjects were planned to be enrolled in Group 4, out of which 15 and 3 subjects were to receive Ad26.ZEBOV and placebo, respectively. Due to the study halt following a case of Miller Fisher syndrome, many subjects did not receive the boost vaccination or had late boost vaccination. Because of this, it will be difficult to evaluate the planned regimens. Therefore, recruitment in the study was stopped and the total sample size reduced to approximately 423 subjects. See Section 11.2 of the CTP for further details.

## 1.5. Randomization and Blinding

Randomization was used to minimize bias in the assignment of subjects to vaccination schedules (groups), to increase the likelihood that known and unknown subject attributes (eg, demographic and baseline characteristics) are evenly balanced across groups, and to enhance the validity of possible statistical comparisons across groups. In addition, randomization was used to minimize bias in the assignment of subjects to study vaccine (active vaccine versus placebo).

Central randomization was implemented in this study. At baseline, subjects were randomly assigned to 1 of 3 groups in a 1:1:1 ratio in Cohorts I, II, and III. Blinding procedure were not applied to Cohort I (as all subjects received Ad26.ZEBOV and MVA-BN-Filo in an open-label fashion). Cohorts II and III were blinded. Within group, subjects were randomly assigned to Ad26.ZEBOV and MVA-BN-Filo, or placebo in a 14:1 and 10:3 ratio in Cohorts II and III, respectively, based on a computer-generated randomization schedule prepared before the start of the study under the supervision of the sponsor. Subjects in Group 4 were randomly assigned (in a blinded fashion) to Ad26.ZEBOV or placebo in a 5:1 ratio. The randomization within each group was balanced by using randomly permuted blocks and was stratified by country in Cohorts II and III. Randomization in each group (for Cohorts II and III) was further stratified by age at randomization ( $\leq 50$  years,  $> 50$  years).

In Cohorts II and III, subjects and study-site personnel were blinded to the study vaccine allocation within groups until the last subject of the study completed the 6-month post-boost visit or discontinued earlier and the clinical database was locked, except for unblinded qualified study-site personnel with primary responsibility for study vaccine preparation and dispensing, and not involved in any other study-related procedure. The study vaccines were administered by a study vaccine administrator (ie, a trained study nurse, medical doctor, or otherwise qualified health care provider who had no other study function).

For Group 4, subjects and study-site personnel were blinded to the study vaccine allocation until the last subject of Group 4 completed the 28-day post-vaccination visit or discontinued earlier and the clinical database was locked, except for unblinded qualified study-site personnel with primary responsibility for study vaccine preparation and dispensing, and not involved in any other study-related procedure.

Data that could potentially unblind the study vaccine assignment (ie, study vaccine preparation/accountability data, immunogenicity data or other specific laboratory data) was handled with special care to ensure that the integrity of the data was maintained and the potential for bias was minimized. This could include making special provisions, such as segregating the data in question from view by the investigators, clinical team, or others as appropriate until the time of database lock and unblinding. The pharmacy and preparation of study vaccines were monitored by an independent study vaccine monitor (ie, an unblinded study vaccine monitor assigned to the study who is responsible for the unblinded interface between the sponsor and the investigational site pharmacy).

## 2. GENERAL ANALYSIS DEFINITIONS

The type I error rate ( $\alpha$ ) is set to 0.05 and corresponding 2-sided 95% confidence intervals (CIs) will be calculated wherever applicable. Adjustment of the  $\alpha$  (type I error) level due to

multiplicity is not applicable for this study as no planned formal statistical hypothesis testing will be performed.

Analysis and evaluation are defined separately for each parameter later in this document together with the description of rules for handling missing or incomplete data. The analyses will include vaccinated subjects with respect to the actual vaccine administered. The subjects who were vaccinated according to MVA-BN-Filo prime/Ad26.ZEBOV boost or a homologous (ie, Ad26.ZEBOV prime/ Ad26.ZEBOV boost or MVA-BN-Filo prime/MVA-BN-Filo boost) schedule will be excluded from summary analyses (ie, tables and graphs) and listed separately.

In general, the study data will be analyzed as follows:

- Categorical variables will be summarized with a frequency table presenting counts and percentages.
- Continuous variables will be summarized using the following statistics, as appropriate: number of observations, arithmetic mean, geometric mean, corresponding 95% confidence interval (CI), standard deviation, standard error, median, quartiles (Q1 and Q3), minimum and maximum.

*Baseline value* will be defined as the value of the last available assessment performed prior to the prime vaccination, unless specified otherwise.

For safety assessments, the *baseline value* will be an assessment performed prior or on the date (if only time of assessment is missing) of the prime vaccination. The baseline value for immunogenicity assessments will be an assessment performed before or on the date of the prime vaccination. In case of multiple values, the value closest to the vaccination will be used as the baseline.

*Reference value* (only for immunogenicity) will be defined as the assessment performed on the date of the boost vaccination. In case of multiple values (on the same day of vaccination), the value closest to the vaccination will be used as the reference value.

*Visit day* will be determined relative to the actual day of vaccination (date of prime vaccination or date of boost vaccination).

Repeated assessments of immunogenicity and safety will be allocated to analysis windows and periods based on [Table 1](#) and [Table 2](#).

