11.1. Analysis Sets

The Full Analysis set includes all subjects who were randomized and received at least one dose of study vaccine, regardless of the occurrence of protocol deviations. Safety data will be analyzed based on the Full Analysis set.

The Immunogenicity analysis set includes all randomized and vaccinated subjects, who have data from baseline and at least one post-vaccination immunogenicity blood draw.

The Per Protocol analysis set includes all randomized and vaccinated subjects, who received both the prime and boost (administered not more than 10 days outside the visit window) vaccinations, have immunogenicity data from baseline and at least one post-vaccination evaluable immunogenicity sample, and have no major protocol violations influencing the immune response.

The immunogenicity analysis will be based on the Per Protocol analysis set. As sensitivity analysis, the immunogenicity data will also be analyzed based on the Immunogenicity analysis set, provided more than 10% of subjects in the Immunogenicity analysis set are excluded from the Per Protocol analysis set.

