## 2.3. Analysis Sets

### Full Analysis Set

The full analysis set includes all subjects who were randomized and received at least 1 dose of study vaccine (Ad26.ZEBOV, MVA-BN-Filo or placebo), regardless of the occurrence of protocol deviations.

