## 7. SAFETY

The safety and tolerability data include the following:

- AEs collected from signing of the informed consent form (ICF) onwards until the 42-day post-boost visit.
- Serious adverse events (SAEs) and immediate reportable events (IREs) from signing of the ICF onwards until the end of the study.
- Solicited local and systemic AEs (reactogenicity) recorded during the first 8 days (including the day of the vaccination) following each vaccination.

The safety and tolerability data will be summarized based on the full analysis set. The analysis will be based on the actual dose (ie, Dose 1 and Dose 2 for the prime and boost vaccinations, respectively) that the subjects received. For example, if Dose 2 is not administered to a subject, then that subject will not be included in the analysis of AEs in the Post-dose 2 period. Focus will be on safety signals detected during the Post-dose 1 and Post-dose 2 periods, as well as the Regimen phase.

- The safety data will be evaluated based on the pooled (matching on vaccination schedules) cohorts II and III. The data will be presented separately for Cohort I and Group 4. See

[Table 4](#) for an overview.

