### 7.1.3. Analysis Methods

In general, the AEs following vaccination will be summarized (ie, tables of descriptive statistics) by vaccination schedule and presented per period/phase. The presentation will be according to the cohorts as shown in

[Table 4](#). Similar summary tables will also be provided pooled by vaccine (dose).

Furthermore, unsolicited AEs will be summarized (showing number and percentage) by System Organ Class (SOC) and Preferred Term (PT). Solicited AEs (recorded by day) will be converted into the analysis format of unsolicited AEs (recorded by event), as detailed in Attachment 2. These solicited AEs will be summarized by class (local, systemic) and Preferred Term. For solicited as well as unsolicited AEs, tables focusing on severity will be created. Focus will also be on the relationship (to the study vaccine) of the solicited systemic and unsolicited AEs.

The SAEs, AEs with fatal outcome, AEs leading to permanent discontinuation from boost vaccine administration, Grade 3 AEs and IREs will also be listed. A table summarizing all those parameters will further be created and presented per analysis period and vaccination schedule. Summary tabulations by SOC and PT for each of the category of events (ie, SAEs, AEs with fatal outcome, AEs leading to permanent discontinuation from boost vaccination, Grade 3 AEs and immediate reportable events) will also be generated on the entire reporting period and presented by vaccination schedule. Subject narratives will be generated for these events, except Grade 3 AEs. For Grade 3 AEs, the narratives will only be generated for those AEs that are considered related to study vaccination.

For the most frequent (at least 10% of subjects in any vaccination schedule) solicited local and systemic AEs, the duration and time to first onset of the events will also be summarized. If a subject experiences more than 1 occurrence of a solicited event, the maximum duration of the events will be used. The time to first onset is defined as:

$$[\textit{date of first onset} - \textit{reference date} + 1]$$

The reference date is the start date of each vaccination period (ie, Post-dose 1 or Post-dose 2). Duration and time to onset of AEs will be expressed in days.

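### The SAP removes reverse-order and homologous vaccinees from all tables and graphs, which conflicts with summarising primary safety on the full analysis set

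*SAP*

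**What the plan says.** SAP section 2 (General Analysis Definitions) sets an as-treated principle: "The analyses will include vaccinated subjects with respect to the actual vaccine administered". The next sentence makes an exception. Subjects given MVA-BN-Filo as prime and Ad26.ZEBOV as boost, or Ad26.ZEBOV twice, or MVA-BN-Filo twice, "will be excluded from summary analyses (ie, tables and graphs) and listed separately". The sentence stands among definitions for the whole analysis and does not mention immunogenicity.

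SAP section 2.3 defines the full analysis set as all randomised subjects who "received at least 1 dose of study vaccine (Ad26.ZEBOV, MVA-BN-Filo or placebo), regardless of the occurrence of protocol deviations". SAP section 7 then states: "The safety and tolerability data will be summarized based on the full analysis set". It adds that the analysis follows the dose actually received, and it names no excluded subjects. The protocol agrees. Section 11.1 says "Safety data will be analyzed based on the Full Analysis set", and section 11.4 puts unsolicited adverse events on the same set and says that all reported adverse events enter the analysis.

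SAP section 3 (Changes to the Planned Analysis) lists the redefinition of the immunogenicity and per protocol sets only. It does not mention removing anyone from the safety tables.

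**The concern.** A subject cannot belong to the set on which safety is summarised and also be absent from every summary. Two programmers working from this SAP could produce different denominators for the same table, and each could point to a sentence that supports the choice.

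Safety and tolerability are the primary objective. Protocol section 12.2 names an administration error with study vaccine among the safety events of interest, yet the rule takes out of the rates subjects in whom such an error may have occurred. Single events also carry weight in this trial: vaccination was halted after one case of Miller Fisher syndrome (SAP section 1). A rule that could turn a count of one into zero in a table therefore deserves attention, even if it is unlikely to be triggered.

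**Working it through.** **Step 1: the texts side by side.**

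- *Who is in the safety set?* Everyone randomised with at least one dose, whatever the deviation (SAP 2.3, protocol 11.1). Receiving the wrong product or order is a deviation, so these subjects are in.
- *What is done with that set?* Safety is summarised on it by actual dose (SAP 7). No exception is stated.
- *Who is left out of tables and graphs?* Reverse-order and homologous vaccinees (SAP 2). The safety tables are tables, so these subjects are out.
- *Is the difference resolved or declared?* Section 7 neither repeats nor overrides the exclusion, and section 3 does not list it.

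**Step 2: what the rule removes.** In SAP Table 2 the Post-dose 1 period ends no later than one minute before Dose 2. For a subject given Ad26.ZEBOV twice, every Post-dose 1 event follows a correctly given Ad26.ZEBOV prime, and the later error cannot have influenced it. The rule still drops that subject from the Post-dose 1 tables. Conversely, the listed sequences all have two doses, so a subject given MVA-BN-Filo as prime and no boost is not covered. How such a subject, or one with a mixed active and placebo sequence, would be shown is not stated.

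**Step 3: size.** The plan gives no figure for this point and no count of affected subjects, so the number excluded, k, is an assumption. Inputs: planned active group sizes of 174 and 121 (protocol 11.2).

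The upper limit when no event is seen (one-sided 97.5%) is 1 − 0.025^(1/N). Checked against protocol 11.2, it gives 3.00%, 2.10% and 0.74% for N = 121, 174 and 499. The protocol says less than 3.3%, 2.2% and 0.8%, so its statements are true.

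*Rare event.* Suppose the only event of its type occurs in an excluded subject of a group of 174.

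- Full analysis set: 1/174 = 0.57% (exact 95% CI 0.01 to 3.16%).
- Table with k = 1: 0/173 = 0%, upper limit 1 − 0.025^(1/173) = 2.11%.
- Table with k = 5: 0/169 = 0%, upper limit 2.16%.

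In a group of 121, the change with k = 1 is from 1/121 = 0.83% to 0/120.

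The 174 includes 10 Cohort I subjects (84 + 80 + 10, protocol Table 1), whom SAP section 7 presents separately. In a pooled Cohort II and III column at planned size the rate would be 1/164 = 0.61%. Actual groups are probably smaller, because SAP section 1.4 reports that the total fell to about 423.

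*Common event.* Suppose 17 of 174 subjects have the event (9.8%) and k = 5.

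- All five excluded subjects had it: 12/169 = 7.1%.
- None of the five had it: 17/169 = 10.1%.

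Rates of common events shift modestly, and only if k is several subjects. A rare event can disappear from the tables with k = 1.

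**The case against.** The best defence is that the two rules work at different levels. The full analysis set defines membership, section 2 governs presentation, and section 2 also says that analyses are defined parameter by parameter later on. On that reading section 7, as the specific section, governs safety. This may be what the sponsor intends. But section 7 contains no override, and the exclusion refers to tables and graphs without qualification. The defence shows that one sentence could settle the matter. It does not show that the matter is settled.

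A second defence is that the primary objective concerns three heterologous schedules. A subject who received none of them has no correct column, and placing the subject under the assigned schedule would attribute events to a regimen not received. The study is descriptive, so no formal comparison is harmed. This is a good reason not to force these subjects into a schedule column, and for by-schedule immunogenicity the exclusion is sensible. For safety it argues for a separate column, not for omission.

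Two stronger readings are tempting, and the documents do not support them. A reader might infer that an SAE, IRE or Grade 3 event in such a subject would be visible only in a listing. SAP section 7.1.3 provides narratives for SAEs, IREs and Grade 3 events considered related, and SAP section 5.1 lists assigned and actual regimens. Such events would be individually visible; what is incomplete is the rates. A reader might also infer that the planned adverse event tables pooled by vaccine (dose) already have a place for these subjects. Section 7 equates Dose 1 with prime and Dose 2 with boost, and no column is stated for MVA-BN-Filo as Dose 1 or Ad26.ZEBOV as Dose 2. A column would have to be added.

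Finally, central randomisation and independent monitoring of vaccine preparation make such errors unlikely. That limits the expected impact but does not remove the contradiction.

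**Conclusion.** The contradiction is real and should be corrected, but it is minor. As written, the rule takes exposed subjects out of the primary safety tables. It does so against the SAP's own safety population and the protocol's, and without declaration in the section on changes. Their data would still be reported through listings and narratives, so nothing is concealed.

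No actual effect on any rate can be claimed, because the number of affected subjects is not given and may be zero. The illustration of 0/173 in place of 1/174 (0.57%) assumes one affected subject, the only event of its type, and the planned group size. The textual finding depends on none of these assumptions.

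**What to change.** Limit the exclusion in SAP section 2 to by-schedule immunogenicity tables and graphs. State in section 7 that all full-analysis-set subjects stay in the safety tables by vaccine (dose) actually received, with an 'other sequence' column where no planned schedule applies. Include them in an overall count of subjects with SAEs, IREs and Grade 3 events, with a footnote giving their number. The same sentence can say how a single wrong prime without boost, or a mixed active and placebo sequence, is handled.

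If the exclusion is meant to cover safety, declare it in SAP section 3 with the reason, and report how many subjects it removes.

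The cost is one SAP sentence plus an added column or footnote in the safety tables. An overall count also has to be specified, because section 7.1.3 presents the SAE, IRE and Grade 3 tables by schedule and names no total across schedules. If no subject is affected, the column can be omitted and the footnote can say so.
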